#### 3.1.2 Treatment Period

Up to 2 weeks after the Screening Visit, participants will return to the site on Day 1 (Visit 2) to be randomized and begin treatment. Approximately 100 eligible participants (25 participants per treatment group) will be randomized in a 1:1:1:1 ratio to 1 of the following treatment groups:

- Combination therapy: 5 mg obicetrapib + 10 mg ezetimibe;
- Obicetrapib monotherapy: 5 mg obicetrapib + placebo ezetimibe;
- Ezetimibe monotherapy: placebo obicetrapib + 10 mg ezetimibe; or
- Placebo: placebo obicetrapib + placebo ezetimibe.

During the 8-week Treatment Period, the assigned study drugs will be administered by the participant orally and once daily on Days 1 through 57. Participants will return to the site every 4 weeks for efficacy, safety, PK, and CETP mass assessments. Participants, Investigators, the Clinical Research Organization, and the Sponsor will be blinded to all lipid results from Day 1 (Visit 2) for the first participant through the PK Visit (Visit 6) for the last participant in order to protect blinding to treatment assignment.

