#### 3.1.3 Safety Follow-up Period

Participants will return to the site for a Safety Follow-up Visit (Visit 5) approximately 4 weeks after the end of the Treatment Period for safety, PK, and CETP mass assessments.

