# 6.4 Safety Follow-up Visit (Visit 5, Day 85 ±3 Days)

The following procedures will be performed at the Safety Follow-up Visit (Visit 5):

- Record concomitant medications;
- Obtain vital signs;
- Collect fasting (≥10 hours) blood samples for chemistry and hematology panels;
- Collect urine sample for urinalysis;
- Collect blood samples for PK and CETP mass and store for future analysis; and
- Assess AEs.

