## 6.5 Pharmacokinetic Visit (Visit 6, Day 113 $\pm$ 7 Days)

The following procedures will be performed at the PK Visit (Visit 6):

- Collect blood samples for PK and CETP mass and store for future analysis; and
- Assess AEs.

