# **APPENDIX A: SCHEDULE OF PROCEDURES**

	Screening Treatment Period			riod	Safety Follow-up PK	PK	Early
Visit	1	2	3	4	5	6	Termination
Week	Up to -2	0	4	8	12	16	Visit
Day (±Visit Window)	-14 to -1	1	29 (±3)	57 (±3)	85 (±3)	113 (±7)	Unscheduled
Informed consent a	X						
Inclusion/exclusion criteria	X	Xb					
Demographic information	X						
Medical/surgical history	X						
Prior/concomitant medications	X	X	X	X	X		X
Weight and height c	X			X			X
Physical examination	X			X			X
Vital signs d	X	X	X	X	X		X
12-lead ECG e	X						
Urine pregnancy test f	X						
FSH test g	X						
Fasting (≥10 hours) chemistry and hematology h	X	X	X	X	X		X
Urinalysis	X	X	X	X	X		X
Fasting (≥10 hours) lipid profile i	X	X	X	X			X
PK sample j		X		X	X	X	
CETP mass sample j		X		X	X	X	
Randomization		X					
Dispense study drugs, as appropriate		X	X				
Study drug administration k		X	X	X			
Study drug compliance check			X	X			X
TLC diet counseling 	X	X	X				
Register visit in IRT	X	X	X	X			X
Adverse event assessment		X	X	X	X	X	X

- a. Signed informed consent must be obtained before any study-related procedures are performed.
- b. Any updates since the Screening Visit will be assessed.
- c. Height and weight will be measured at the Screening Visit and will be used to calculate body mass index. Weight only will be measured at all other visits as indicated. Measurement of weight should be performed with the participant dressed in indoor clothing, with shoes removed, and bladder empty.
- d. Vital signs will include body temperature, heart rate, and triplicate blood pressure (systolic and diastolic) measurements.
- e. A single, standard 12-lead ECG will be performed by the Investigator or trained site personnel at the Screening Visit and centrally read by
- f. For women of childbearing potential only.
- g. FSH test will be performed in peri-menopausal women, defined as women <55 years of age for whom it has been ≥1 year since their last menstrual period.
- h. At Screening Visit only, hematology panel will include HbA1c.
- i. At all visits, LDL-C will be calculated using the Friedewald formula. In addition, at Visit 2 and Visit 4, LDL-C will also be measured by preparative ultracentrifugation, also referred to as beta quantification.
- j. Samples will be stored for future analysis.

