3.4 Efficacy Assessment

The mITT Population will be the primary population for the efficacy analyses. Efficacy will also be analyzed using the ITT Population and the PP Population as supportive analyses for select endpoints.

It is to highlight that LDL-C level will be collected using the following two approaches:

- 1. At each scheduled visit, LDL-C level will be calculated using the Friedewald formula;
- 2. In addition, at Baseline (Day 1) and at the end of the 8-week Treatment Period (Day 57), LDL-C will be measured for all patients by PUC¹.
- 3.4.1 Primary Efficacy Endpoint

Primary Analysis

The primary efficacy analysis is to evaluate the percent change from Day 1 to Day 57 in LDL-C (as determined by the Friedewald formula) for the combination therapy group compared to the placebo group. The percent change is calculated from Baseline to each measurement taken at Day 29, Day 57, and Day 85.

The percent change in LDL-C from Day 1 to Day 57 for each treatment is defined mathematically as μ_{jt} , where j stands for the jth treatment (*j*=0,1,2,3) and the subscript 0 refers to the placebo group; and *t* stands for time to visit at Day 29, Day 57, and Day 85 (*t*=1,2,3). The hypotheses testing to the percent change in LDL-C from Day 1 to Day 57 is then defined statistically as following:

 $H_0: \mu_{jt} - \mu_{0t} = 0, H_1: \mu_{jt} - \mu_{0t} \neq 0$, where *j*=1,2,3

NewAmsterdam Pharma BV	
Protocol TA-8995-303	

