In the third sensitivity analysis, the percent change from Day 1 to Day 57 in LDL-C will be assessed where the LDL-C values will be measured by preparative ultracentrifugation (PUC), also referred to as beta quantification. The percent change from Day 1 to Day 57 in LDL-C by PUC for the combination therapy group compared to the placebo group will be analyzed using an ANCOVA similar to the model described in the second sensitivity analysis. No imputation of missing data will be performed for this sensitivity analysis.

In the fourth sensitivity analysis, a similar ANCOVA model as described above will be utilized for the assessment of percent change from Baseline to Day 57 in LDL-C as measured by PUC. In this analysis, missing data at Day 57 will be imputed using a last observation carried backward (LOCB) approach in which the next available LDL-C measurement, as measured by PUC, following Day 57 will be used in the analysis. The previous TULIP trial¹ observed similar values of percent change in LDL-C at Week 8 and 12, providing a rationale for the LOCB approach in this trial.

The ANCOVA model will be implemented using SAS[®] Proc GLM. The sample SAS code can be found below:

Note: USUBJID = unique subject identifier TREATMENT = 0 (Placebo), 1 (Ezetimibe monotherapy), 2 (Obicetrapib monotherapy), 3 (Combination therapy) BASE = Baseline value PCHG = Percent change from Baseline proc glm data=LDL_C; class TREATMENT; model PCHG = TREATMENT BASE / ss1 ss3; means TREATMENT;

NewAmsterdam Pharma BV Protocol TA-8995-303	CONFIDENTIAL	Statistical Analysis Plan Version V2.0, 24 June 2021
Ismeans TREATMENT / cov stder estimate " Ezetimibe monother estimate " Obicetrapib monoth estimate " Combination therap	apy: Placebo" TREATMENT - nerapy: Placebo" TREATMENT -	1010;
run;		

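### Two sensitivity analyses in SAP 3.4.1 were not aligned with protocol v4.0: the PUC carry-back has no scheduled later value, and the placebo-based imputation names a Day 85 LDL-C that v4.0 does not schedule

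*SAP*

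**What the plan says.** **Fourth sensitivity analysis (SAP 3.4.1).** Percent change in PUC LDL-C is analysed by ANCOVA. For a missing Day 57 value, "the next available LDL-C measurement, as measured by PUC, following Day 57 will be used in the analysis". The reason given is that the earlier obicetrapib trial "observed similar values of percent change in LDL-C at Week 8 and 12, providing a rationale for the LOCB approach". The third sensitivity analysis is the same PUC ANCOVA without imputation.

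**PUC schedule.** SAP 3.4 says that at Baseline and "at the end of the 8-week Treatment Period (Day 57), LDL-C will be measured for all patients by PUC". Protocol Appendix A, footnote i, agrees: "In addition, at Visit 2 and Visit 4, LDL-C will also be measured by preparative ultracentrifugation". SAP Appendix B repeats it.

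**Visits after Day 57 in the supplied protocol.** The visit days match the SAP's v4.0 window table, so I take this to be v4.0. Visit 5 is "Safety Follow-up Visit (Visit 5, Day 85 ±3 Days"), held "approximately 4 weeks after the end of the Treatment Period for safety, PK, and CETP mass assessments". Its procedure list has no lipid profile. At Visit 6 the only blood sampling is "Collect blood samples for PK and CETP mass and store for future analysis; and". On dosing, "the assigned study drugs will be administered by the participant orally and once daily on Days 1 through 57".

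**First sensitivity analysis (SAP 3.4.1).** A placebo-based multiple imputation covers missing LDL-C at Days 29, 57 and 85, with those three visits and Baseline as model variables. It starts from 25 data sets, with more if the percentage of incomplete cases exceeds what was anticipated.

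**Two protocol versions (SAP 3.1.2).** The v3.0 window table has an analysis visit named Day 85, followed by Safety Follow-up at Day 113 and PK at Day 141. In the v4.0 table the row with target day 85 (Days 72 to 99) is Safety Follow-up. SAP section 5 says the SAP does not depart from protocol v4.0.

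**The concern.** These are the only two of the four sensitivity analyses that impute missing data, so they carry the missing-data check on the primary endpoint. Both refer to measurements that v4.0 does not schedule.

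A carry-back with nothing to carry back is not a test of missing PUC data. If it were reported beside the third analysis, the agreement of the two could be taken for robustness when they are the same calculation.

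In the imputation, a Day 85 step that depends on an unstated number of v3.0 placebo participants may fail to fit and then need an unplanned change after unblinding. Counting an unscheduled visit as missing would also make the incomplete-case percentage reflect protocol version more than dropout.

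**Working it through.** **1. The plan's own figure.** With 25 per arm and SD 15, the standard error of a difference is 15 × √(2/25) = 4.24 points. A 30-point difference is 30/4.24 = 7.07 standard errors, and power is above 0.9999, so the stated >90% holds. The point does not depend on it; the 30 points only give a scale.

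**2. Schedule under v4.0.**

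| Visit | LDL-C (Friedewald) | PUC |
|---|---|---|
| Day 1 (Visit 2) | yes | yes |
| Day 29 (Visit 3) | yes | no |
| Day 57 (Visit 4) | yes | yes |
| Day 85 (Visit 5) | no | no |
| Day 113 (Visit 6) | no | no |
| Early termination | yes | not listed |

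Scheduled PUC values after Day 57: 0. Scheduled LDL-C values at Day 85 by any method: 0. Only an early-termination visit falling in Days 72 to 99 could give a v4.0 participant a Friedewald value near Day 85.

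**3. Can the Day 85 step be fitted?** The documents do not give the number enrolled under v3.0. I assume that unscheduled values are treated as missing and that Day 85 is regressed on Baseline, Day 29 and Day 57. That is 4 coefficients, so at least 5 placebo participants with a Day 85 value are needed. With N v3.0 participants spread evenly over four arms and dropout d, P(not fittable) = P(Binomial(N/4, 1−d) ≤ 4):

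| N under v3.0 | Placebo | d = 5% | d = 10% | d = 15% |
|---|---|---|---|---|
| 40 | 10 | <0.1% | <0.1% | 0.1% |
| 32 | 8 | <0.1% | 0.5% | 2.1% |
| 24 | 6 | 3.3% | 11% | 22% |
| 20 | 5 | 23% | 41% | 56% |
| 16 | 4 | 100% | 100% | 100% |

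If v3.0 membership is instead random among 25 placebo participants with no dropout, P(Binomial(25, q) ≤ 4) at v3.0 shares q of 10, 20, 30 and 50% is 90, 42, 9 and <0.1%.

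**4. Incomplete cases, if Day 85 counts for v4.0.** Share = s + (1−s) × d, where s is the v4.0 share. At d = 10% and s = 25, 50, 75 and 100%: 0.25 + 0.75 × 0.10 = 32.5%, then 55, 77.5 and 100%. Counting scheduled visits only, it is 10%.

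**5. Effect where the step can be fitted.** This illustrative simulation compares Day 85 imputed for everyone with Day 85 left as observed, using the same Day 29 and Day 57 draws.

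- Design: 25 per arm; baseline LDL-C normal (135, 20) mg/dL truncated to 100–175; percent-change SD 15; between-visit correlation 0.6; arm means 0, −15, −25 and −30.
- Missing data: 10% missing from Day 57 on, half of them also at Day 29; v4.0 membership random.
- Analysis: 25 imputations, unstructured REML MMRM, Rubin pooling, 300 trials per row.

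| v4.0 share | Mean shift | Mean absolute shift | 95th percentile of absolute shift | Median SE ratio | Not fittable |
|---|---|---|---|---|---|
| 25% | 0.003 | 0.07 | 0.27 | 1.00 | 0/300 |
| 50% | −0.001 | 0.10 | 0.39 | 1.00 | 2/300 |
| 75% | 0.068 | 0.32 | 1.24 | 1.01 | 100/300 |
| 80% | −0.013 | 0.47 | 1.70 | 1.02 | 165/300 |

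Shifts are in percentage points and describe fitted trials only. The smallest |estimate|/SE was 3.02, so no conclusion changed. The last column (33% and 55% in the lower rows) exceeds the even-split figures in step 3 because placebo membership of v3.0 varied at random. The matching binomials agree: P(Binomial(25, 0.25 × 0.9) ≤ 4) = 31% and P(Binomial(25, 0.20 × 0.9) ≤ 4) = 52%.

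**The case against.** The strongest reply is that the SAP serves two protocol versions and we can see only one. The v3.0 windows have a Day 85 visit before a Safety Follow-up at Day 113, and the exposure categories in SAP 3.3.7 run to 12 weeks. That suggests, without proving it, that v3.0 treatment ran longer. If so, the Week 8/Week 12 rationale may suit v3.0 participants. This stands. A reader might infer that the fourth analysis is empty for everyone. The documents do not support that, because a later v3.0 PUC value can be neither confirmed nor excluded.

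Second, the SAP says missing data will be imputed. It does not say that a visit never scheduled for a participant is missing. This also stands: steps 3 to 5 hold only under the wider reading, and a programmer could reasonably take the narrower one.

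Third, the consequence is small. Raising the number of imputations does no harm, the anticipated percentage is not stated, and a model that cannot be fitted would be noticed in programming. That lowers the priority, but it does not make the carry-back work for v4.0 participants.

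The rationale does not rescue the rule under v4.0. Dosing ends on Day 57 and Week 12 is about 4 weeks after treatment; nothing in the documents says that the earlier trial's Week 12 values were taken off drug.

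**Conclusion.** The misalignment is real and limited to two supportive analyses.

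- **Fourth analysis:** for v4.0 participants the carry-back has no scheduled donor and the result equals the third. This follows from the schedule without assumptions. For v3.0 participants it is undetermined.
- **First analysis:** Day 85 is named where v4.0 schedules no LDL-C. If unscheduled values count as missing, the step depends almost entirely on v3.0 placebo participants and may not be fittable at about 5 or fewer. Where it can be fitted, the illustrative mean shift is within 0.07 points on 30. Single-trial shifts grow as v3.0 participants become fewer, with a 95th percentile of 1.70 points at an 80% v4.0 share. All these figures rest on an assumed v3.0 headcount, dropout rate and correlation.

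Because Day 85 also appears in the primary hypotheses and the MMRM, a reader might infer that the primary result is compromised. The documents do not support that. The MMRM uses all available values, so v4.0 participants contribute none at Day 85, and no effect on the Day 57 contrast or the ranked secondary tests is shown. The simulation compared two imputation variants and did not test the primary model.

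The priority lies between a minor clarification and a change that should be made.

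**What to change.** 1. **First sensitivity analysis.** Impute LDL-C at Day 29 and Day 57 only, for all participants. Use an observed Day 85 value as a predictor only where it exists, and leave it out if there are too few placebo values to support it. Leave Day 85 as observed or absent in the MMRM. Do not count Day 85 as incomplete data for v4.0 participants when setting the number of imputations.
2. **Fourth sensitivity analysis.** Replace the carry-back with multiple imputation of missing Day 57 PUC from treatment, baseline PUC and the available Friedewald LDL-C (Baseline and Day 29 only, if the Day 57 visit was missed). If the carry-back is kept, limit it to v3.0 participants with a later on-treatment PUC value, and report the number filled by arm.
3. **Schedule.** State which LDL-C and PUC visits apply under each protocol version and the v3.0 headcount by arm, and correct SAP section 5 if needed.

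The cost is SAP wording and minor programming, with no new data. The PUC imputation brings a missing-at-random assumption, which should be stated.

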3.4.2 Secondary Efficacy Endpoints

Similar MMRM models will be developed to examine the percent change from Day 1 to Day 57 in LDL-C (by Friedewald formula) or ApoB. In order to maintain the overall Type I error rate, the secondary efficacy endpoints will be tested sequentially at the 0.05 significance level according to the pre-specified order of hierarchy.

- Percent change from Day 1 to Day 57 in LDL-C for the obicetrapib monotherapy group compared to the placebo group;
- Percent change from Day 1 to Day 57 in ApoB for the combination therapy group compared to the placebo group;
- Percent change from Day 1 to Day 57 in ApoB for the obicetrapib monotherapy group compared to the placebo group;
- Percent change from Day 1 to Day 57 in LDL-C for combination therapy group compared to the ezetimibe monotherapy group;
- Percent change from Day 1 to Day 57 in LDL-C for the obicetrapib monotherapy group compared to the ezetimibe monotherapy group;
- Percent change from Day 1 to Day 57 in LDL-C, for the ezetimibe monotherapy group compared to the placebo group; and
- Percent change from Day 1 to Day 57 in ApoB for the combination therapy group compared to the ezetimibe monotherapy group.

3.4.3 Exploratory Efficacy Endpoints

Similar MMRM models will be used for the following analysis:

- Percent change from Day 1 to Day 57 in ApoB for the ezetimibe monotherapy group compared to the placebo group;
- Pairwise comparisons among the various treatment groups for the percent change from Day 1 to Day 57 in non-HDL-C, VLDL-C, HDL-C, TG, ApoE, and HDL-ApoE (with and without ApoC3);
- Pairwise comparisons among the various treatment groups for the change from Day 1 to Day 57, Day 1 to Week 12, and Day 1 to Week 16 in the mean trough plasma levels of obicetrapib; and
- Pairwise comparisons among the various treatment groups for the change from Day 1 to Day 57, Day 1 to Week 12, and Day 1 to Week 16 in CETP mass.

The proportion of subjects at Day 57 that achieve LDL-C <2.6 mmol/L (<100 mg/dL), LDL-C <1.8 mmol/L (<70 mg/dL), and LDL-C <1.3 mmol/L (<50 mg/dL) will be examined through Logistic Regression Models for binary variables with covariates of the treatment groups and the Baseline variable.

The Logistic Regression Model will be implemented using SAS[®] Proc LOGISTIC. The sample SAS code can be found below:

NewAmsterdam Pharma BV	CONFIDENTIAL	Statistical Analysis Plan		
Protocol TA-8995-303		Version V2.0, 24 June 2021		

Note: USUBJID = unique subject identifier TREATMENT = 0 (Placebo), 1 (Ezetimibe monotherapy), 2 (Obicetrapib monotherapy), 3 (Combination therapy) BASE = Baseline value LDLC100 = LDL_C value less than 100mg/dL at DAY57 (YES/NO) for example proc logistic data= LDL_C; Class TREATMENT(ref=0) / Param= Ref; Model LDLC100 = TREATMENT BASE / alpha=0.05 expb plcl plrl orpvalue lackfit; Ods output ParameterEstimates= Log_LDLC100_ParameterEstimates CLoddsPL= Log_ LDLC100_OddsRatios ; Run;

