## 7 EFFICACY ASSESSMENTS

The primary efficacy endpoint is percent change from Day 1 to Day 57 in LDL-C for the combination therapy group compared to the placebo group.

The secondary efficacy endpoints include the following, in hierarchical order:

- Percent change from Day 1 to Day 57 in LDL-C for the obicetrapib monotherapy group compared to the placebo group;
- Percent change from Day 1 to Day 57 in ApoB for the combination therapy group compared to the placebo group;
- Percent change from Day 1 to Day 57 in ApoB for the obicetrapib monotherapy group compared to the placebo group;
- Percent change from Day 1 to Day 57 in LDL-C for the combination therapy group compared to the ezetimibe monotherapy group;
- Percent change from Day 1 to Day 57 in LDL-C for the obicetrapib monotherapy group compared to the ezetimibe monotherapy group;
- Percent change from Day 1 to Day 57 in LDL-C for the ezetimibe monotherapy group compared to the placebo group; and
- Percent change from Day 1 to Day 57 in ApoB for the combination therapy group compared to the ezetimibe monotherapy group.

The exploratory efficacy endpoints include the following:

- Percent change from Day 1 to Day 57 in ApoB for the ezetimibe monotherapy group compared to the placebo group;
- Pairwise comparisons among the various treatment groups for the percent change from Day 1 to Day 57 in non-HDL-C, VLDL-C, HDL-C, TG, ApoE, and HDL-ApoE (with and without ApoC3);
- Pairwise comparisons among the various treatment groups for the proportion of participants at Day 57 that achieve LDL-C <2.6 mmol/L (<100 mg/dL), LDL-C <1.8 mmol/L (<70 mg/dL), and LDL-C <1.3 mmol/L (<50 mg/dL);

- Pairwise comparisons among the various treatment groups for the change from Day 1 to Day 57, Day 1 to Week 12, and Day 1 to Week 16 in the mean trough plasma levels of obicetrapib; and
- Pairwise comparisons among the various treatment groups for the change from Day 1 to Day 57, Day 1 to Week 12, and Day 1 to Week 16 in CETP mass.

Blood samples for lipid profile must be obtained under fasting conditions (ie, after the participant has fasted for  $\geq 10$  hours). For the purposes of this study, fasting will be defined as nothing by mouth except water and any essential medications. If a participant is not fasting, the Investigator will reschedule the visit as soon as possible.

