#### 9 STATISTICS

# 9.1 Analysis Populations

The Intent-to-Treat (ITT) Population will include all participants randomized into the study. Treatment classification will be based on the randomized treatment.

The Modified ITT (mITT) Population will include all participants in the ITT Population who receive at least 1 dose of any study drug and have a baseline value for the LDL-C assessment. Any efficacy measurement obtained after a participant receives a restricted lipid-altering therapy, outside of the current study design, will be removed from the mITT analysis. Treatment classification will be based on the randomized treatment. The mITT Population will be used for the primary analysis of all efficacy endpoints.

The Per-Protocol (PP) Population will include all participants in the mITT Population who have a baseline value for the LDL-C assessment, have a Day 57 value for the LDL-C assessment, and who did not experience a major protocol deviation that potentially impacted the primary efficacy endpoint. The PP Population, along with the reason for exclusion, will be finalized prior to study unblinding.

The PK Population will include all participants in the mITT Population who have sufficient blood samples collected for valid estimation of PK parameters.

The Safety Population will include all participants who receive at least 1 dose of any study drug. Treatment classification will be based on the actual treatment received. The Safety Population will be the primary population used for the safety analyses.

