2.2 Study Design

2.2.1 Overview

This study will be a placebo-controlled, double-blind, randomized Phase 2 study in participants with mild dyslipidemia to evaluate the efficacy, safety, and tolerability of obicetrapib and ezetimibe combination therapy. The study will take place at approximately 10 to 15 sites in North America and Europe as appropriate.

This study consists of a Screening Visit (Visit 1), a Treatment Period (8 weeks, Visits 2 to 4), a Safety Follow-up Visit (Visit 5), and a Pharmacokinetic Visit (Visit 6). The expected study duration for participants entering on the study since Screening Visit is approximately 20-weeks. Please refer to Table 1. Schedule of Procedures) below for details.

At the Screening Visit (Visit 1), participants will be required to sign an informed consent form (ICF) before any study-related procedures are performed. After signing the ICF, participants will be assessed for study eligibility. Participants will also receive counselling regarding the Therapeutic Lifestyle Changes diet and will receive instructions on how to follow this diet. Participants will be required to begin the diet starting at the Screening Visit.

Up to 2 weeks after the Screening Visit, participants will return to the site on Day 1 (Visit 2) to be randomized and begin treatment. Approximately 100 eligible participants (25 participants per treatment group) will be randomized in a 1:1:1:1 ratio to 1 of the following treatment groups:

- Combination therapy: 5 mg obicetrapib + 10 mg ezetimibe;
- Obicetrapib monotherapy: 5 mg obicetrapib + placebo ezetimibe;
- Ezetimibe monotherapy: placebo obicetrapib + 10 mg ezetimibe; or
- Placebo: placebo obicetrapib + placebo ezetimibe.

During the 8-week Treatment Period, the assigned study drugs will be administered by the participant orally and once daily on Days 1 through 57. Participants will return to the site every 4 weeks for efficacy, safety, pharmacokinetics (PK), and CETP mass assessments.

Participants will return to the site for a Safety Follow-up Visit (Visit 5) approximately 4 weeks after the end of the Treatment Period for safety, PK, and CETP mass assessments.

Participants will return to the site for a PK Visit (Visit 6) approximately 8 weeks after the end of the Treatment Period for PK and CETP mass assessments.

CONFIDENTIAL

Table 1. Schedule of Procedures

	0	Т	reatm		Safety	DIC	
N 12 - 14	Screening		Perio		Follow-up	PK	Early
Visit	1	2	3	4	5	6	Termination
Week	Up to -2	0	4	8	12	16	Visit

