3.1.5 Missing Data

Date Values

In cases of incomplete dates (e.g. AE, concomitant medication, and medical history start and/or stop dates), the missing component(s) will be assumed as the most conservative value possible. For example, if the start date is incomplete, the first day of the month will be imputed for the missing day and January will be imputed for the missing month. If a stop date is incomplete, the last day of the month will be imputed for the missing day and December will be imputed for the missing month. Incomplete start and stop dates will be listed as collected without imputation.

Date imputation will only be used for computational purposes such as treatment-emergent status. Actual data values, as they appear in the original CRFs, will be presented within the data listings.

Non-Date Values

For sensitivity analyses of the primary efficacy endpoint, missing values will be imputed using multiple imputation (see Section 3.4.1). For the analyses of secondary and exploratory efficacy endpoints, no imputation will be made for missing values. Safety data will be used according to availability, with no imputation for missing data.

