3.2.2 Modified Intent-to-Treat (ITT) Population

The Modified ITT (mITT) Population will include all participants in the ITT Population who receive at least 1 dose of any study drug and have a Baseline value for the LDL-C assessment. Any

NewAmsterdam Pharma BV	CONFIDENTIAL	Statistical Analysis Plan
Protocol TA-8995-303		Version V2.0, 24 June 2021

efficacy measurement obtained after a participant receives a restricted lipid altering therapy¹, outside of the current study design, will be removed from the mITT analysis. Treatment classification will be based on the randomized treatment. The mITT Population will be used for the primary analysis of all efficacy endpoints.

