The primary efficacy analysis of the percent change from Day 1 to Day 57 in LDL-C will be performed using a mixed model for repeated measures (MMRM) approach. The analysis will include fixed effects for treatment, visit, and treatment-by-visit interaction, along with a covariate of the Baseline value as a continuous covariate. It is to note that randomization was stratified by categories of LDL-C value (<3.5 mmol/L [<135 mg/dL] or \ge 3.5 mmol/L [\ge 135 mg/dL]) only to ensure similar distribution of LDL-C across all treatment groups; however, the MMRM model will include the original scale of the LDL-C value as a continuous covariate. The Restricted Maximum Likelihood estimation approach will be used with an unstructured covariance matrix. The least squares means, standard errors, and 2-sided 95% confidence intervals for each treatment group, for the pairwise comparisons of the combination therapy, obicetrapib monotherapy, and ezetimibe monotherapy to placebo, and for the pairwise comparisons of combination therapy and obicetrapib monotherapy versus ezetimibe monotherapy will be provided. The treatment comparison will be performed using a 2-sided test at the $\alpha = 0.05$ level of significance.

The MMRM approach will include all available assessments of percent change in LDL-C from Baseline to Day 29, Day 57, and Day 85. The model assumes the data are missing at random (MAR). If any data are missing, the model will use all information from the other time points to estimate the mean treatment difference at the given time point. No imputation of missing data will be performed for the primary efficacy endpoint analysis.

The analysis will be implemented using SAS[®] Proc Mixed. The sample SAS code can be found below:

Note: USUBJID = unique subject identifier TREATMENT = 0 (Placebo), 1 (Ezetimibe monotherapy), 2 (Obicetrapib monotherapy), 3 (Combination therapy) VISIT = visit BASE = Baseline value PCHG = Percent change from Baseline proc mixed; class USUBJID TREATMENT VISIT; model PCHG = TREATMENT VISIT; model PCHG = TREATMENT BASE VISIT TREATMENT*VISIT / solution cl; Repeated VISIT / TYPE=UN sub=USUBJID; Ismeans VISIT*TREATMENT / cl diffs; run;

Sensitivity Analysis

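### If the two arms given no obicetrapib enter the trough-level MMRM near zero, combination versus obicetrapib monotherapy has about 17% type I error; fit it in the two dosed arms only.

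*SAP*

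**What the plan says.** - **Endpoint and model.** SAP 3.4.3 opens its list with "Similar MMRM models will be used for the following analysis". The list includes pairwise group comparisons of change by Day 57 and over "Day 1 to Week 12, and Day 1 to Week 16 in the mean trough plasma levels of obicetrapib". Protocol section 7 places the same measure ("Day 1 to Week 16 in the mean trough plasma levels of obicetrapib") among the exploratory efficacy endpoints.
- **Template.** The only MMRM written out is the sample code in SAP 3.4.1. It codes four treatment levels and uses "Repeated VISIT / TYPE=UN sub=USUBJID" with no grouping by arm, so one unstructured matrix serves all four.
- **Arms.** Two of the four receive no obicetrapib: "Ezetimibe monotherapy: placebo obicetrapib + 10 mg ezetimibe" and the placebo arm (SAP 2.2.1). The schedule (Protocol Appendix A) lists PK samples at Day 1, Day 57, Week 12 and Week 16 without restriction by arm, to be stored for later analysis.
- **Population.** SAP 3.2.2 states: "The mITT Population will be used for the primary analysis of all efficacy endpoints". Protocol 9.1 has a separate set: "The PK Population will include all participants in the mITT Population who have sufficient blood samples collected for valid estimation of PK parameters". Protocol 9.2.3 uses that set for descriptive summaries of obicetrapib concentration and for unspecified exploration of exposure relationships. SAP 3.2 defines ITT, mITT, PP and Safety populations but no PK Population, while SAP section 5 reports no departure from protocol v4.0.
- **Missing and unquantifiable values.** SAP 3.1.5 states: "For the analyses of secondary and exploratory efficacy endpoints, no imputation will be made for missing values". Neither document says how concentrations below quantification are handled.

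**The concern.** A shared residual variance is reasonable for LDL-C, which varies in every arm. Obicetrapib concentration is different: participants who never receive the drug should have levels near zero and almost no spread. Read literally, the template averages that near-zero variance with the real variance of the dosed arms and uses the average for every contrast.

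The contrast that suffers is combination versus obicetrapib monotherapy. It is the only one of the six between two dosed arms, so it is the one a reader would use to judge whether ezetimibe changes obicetrapib exposure. If its standard error is too small, chance variation can look like an interaction.

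**Working it through.** **The plan's own figure.** The documents give no power or error rate for the trough comparison. The one stated figure is more than 90% power for LDL-C with 25 per arm, difference 30, SD 15 and two-sided 0.05 (SAP 2.2.4). The noncentrality is 30/(15 × √(2/25)) = 7.07, which gives power above 99.99%. The statement holds, and it confirms the 25 per arm used below.

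**Inputs.** Four arms of 25 (SAP 2.2.1, 2.2.4); two-sided 0.05, with nominal p-values for exploratory endpoints (Protocol 9.2.1.2); one covariance matrix for all arms (SAP 3.4.1). Assumed: undosed values are assayed and entered near zero, and the two dosed arms share a true variance σ².

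**Step 1, pooled variance.** With complete data and treatment-by-visit means, the contrast at each visit equals that from a four-arm one-way ANOVA. Each arm contributes 24 df. Expected pooled variance = (24σ² + 24σ² + 0 + 0)/96 = σ²/2. The standard error of the dosed-arm contrast is therefore √(1/2) = 0.707 of its proper value.

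**Step 2, type I error.** The four-arm statistic is √2 times the proper two-arm t on 48 df, but it is compared with t(0.975, 96) = 1.985. Type I error = 2 × P(T48 > 1.985/√2) = 2 × P(T48 > 1.404) = 16.7%.

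**Step 3, interval width.** 1.985/(√2 × 2.011) = 0.698, where 2.011 = t(0.975, 48). At an assumed CV of 50%, the proper half-width is 2.011 × 0.50 × √(2/25) = 28% of the mean; the four-arm model reports 20%. At CV 30% it is 17% against 12%, and at CV 70%, 40% against 28%.

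**Step 4, undosed arms not exactly zero.** With undosed SD equal to r times the dosed SD, the pooled variance is about σ²(1 + r²)/2. Simulated type I error (normal data, 100,000 trials per setting):

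| r | Four arms | Two dosed arms only |
|---|---|---|
| 0 | 16.6% | 4.9% |
| 0.10 | 16.4% | 5.0% |
| 0.25 | 15.4% | 5.1% |
| 0.50 | 12.0% | 4.9% |
| 0.75 | 8.2% | 5.0% |
| 1.00 | 5.0% | 5.0% |

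**Step 5, robustness.**
- Lognormal dosed arms at CV 30%, 60% and 100%, undosed at zero: 16.7%, 17.0% and 17.0%. Two dosed arms only: 5.0%, 4.7% and 4.4%.
- Only 12 participants per undosed arm contributing values: 10.5%.
- Three-visit REML MMRM with about 4% dropout per visit (2,000 trials, simulation error about 0.8 points): 17.7%, 17.3% and 18.3% at Day 57, Week 12 and Week 16. Two dosed arms only: 4.6%, 4.8% and 5.7%.
- Three-visit REML MMRM with complete data (9,787 trials): 16.0%, with simulation error √(0.16 × 0.84/9,787) = 0.4 points.

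**Step 6, other contrasts.** For dosed versus undosed, the true variance of the difference is σ²/25. The model uses 2 × (σ²/2)/25, which is the same. Simulated type I error is 5.2%.

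**The case against.** The best reply is that four arms are inferred, not specified. SAP 3.4.3 says the models are similar, not identical. The code is a sample for percent change, and the trough endpoint is a change, so the code must be altered anyway. SAP section 6 leaves detail to separate programming specifications. The protocol's more specific rule bases concentration summaries on the PK Population, and someone given no obicetrapib arguably has no PK parameter to estimate. The documents also do not commit to assaying stored samples from the undosed arms. If those arms are left out, the type I error is about 5%.

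All of that stands, and it makes the problem conditional. It does not settle the matter, because SAP 3.2 omits the PK Population, SAP 3.2.2 assigns mITT to all efficacy endpoints, and SAP 3.4.3 asks for comparisons among the groups.

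The consequence is also limited. The endpoint is exploratory with nominal p-values, and neither document plans a conclusion about an interaction. Group means and SDs will be reported, so a reader could notice an interval that is too narrow.

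A reader might also count the baseline covariate as a defect, since the pre-dose level should be about zero in everyone. It is not one: a constant covariate is collinear with the intercept and changes no contrast.

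**Conclusion.** The concern holds conditionally. If undosed-arm concentrations are assayed and entered near zero in a four-arm model with a shared covariance matrix, combination versus obicetrapib monotherapy has about 17% type I error and an interval about 0.70 of the proper width. This rests on 25 per arm and equal true variance in the two dosed arms; it does not depend on the size of that variance. The error falls towards 5% as the undosed arms' variance approaches that of the dosed arms, and it disappears if those arms are left out.

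A reader might infer that the planned analysis certainly pools in this way, or that the trial's main conclusions are at risk. The documents support neither. They do not fix the arms, the population or the treatment of values below quantification for this endpoint. Point estimates with complete data, dosed versus undosed contrasts, and all primary and secondary results are unaffected. This is a worthwhile, low-cost correction to one exploratory analysis.

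**What to change.** - **SAP 3.4.3:** state that the inferential comparison of obicetrapib trough is fitted to the combination and obicetrapib monotherapy arms only, keeping Day 57, Week 12 and Week 16. Summarise the ezetimibe and placebo arms descriptively. A log-scale analysis of post-dose levels, reported as a geometric mean ratio with 95% CI, is optional; the untransformed two-arm analysis already holds its level.
- **SAP 3.2:** add the protocol's PK Population, and reconcile SAP 3.2 and 3.4.3 with Protocol 9.1 and 9.2.3.
- **Values below quantification:** state a rule that covers pre-dose samples. If these were all set to missing, with no imputation under SAP 3.1.5, change from Day 1 could not be computed.

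Keeping four arms with a separate covariance matrix per arm is less safe, because a matrix may not be estimable where an arm has no variance.

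**Cost.** SAP wording and programming only. Residual df for the contrast fall from 96 to 48, so the critical value rises from 1.985 to 2.011 (2.011/1.985 = 1.013). Tests of dosed against undosed arms are given up, but those differences are built into the design.
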